4.3.1 Primary Objectives

The primary objective is to compare outcomes of the three intervention groups, measured a The opioid use and DSM-5 diagnosis of opioid use disorder via modified CIDI-2 Substance Abuse Module at 6-months post-intervention.

4.3.2 Secondary Objectives

Secondary objectives include: (1) HIV risk behaviors (compared using repeated measures procedures to evaluate possible change in sexual and drug-related behaviors that may inhibit or promote HIV infection) measured by the HIV-GAIN; (2) Self-reported number of days incarcerated during the intervention and follow-up phases; (3) Self-reported number of days of opioid and other drug use measured by TLFB, and objective measures of drug use by urine drug screens (UDS) at the 6-month post-release assessment (end of the intervention phase); (4) Self-reported days in drug abuse treatment; (5) Self-reported number of arrests; (6) Self-reported craving for opioids, and (7) Self-reported number of overdoses.

5.0 STUDY DESIGN

5.1 Overview of Study Design

The proposed four-year study is a randomized, open-label trial that will examine feasibility, efficacy, and net economic benefits of a depot medication for opioid addiction, alone or in conjunction with PN, and a drug-education condition receiving no medication. All participants receive standard medical management. Before discharge from jail, participants randomized to one of two medication conditions (VI, PNV) receive Vivitrol and subsequent injections every four weeks for 24 weeks. Those in the PNV condition will meet with a PN before discharge and regularly after release to discuss barriers to treatment, possible treatment program participation following release, and will address social support and other participant needs. Before discharge, the Drug Education (DE) group will participate in session(s) designed to provide a presentation and discussion of drug-related issues. Following release from jail, all participants will receive phone calls from the study team to facilitate scheduling of appointments to occur twice monthly for the first 3 months after release then monthly for the last 3 months of the intervention phase for medical management and to complete assessments. The study nurse will also contact study participants to assess well-being and adverse events.

5.2 Duration of Study and Clinic Visit Schedule

The duration of this study will include a projected 2-4 weeks for screening/baseline assessments and medication induction, and a 24-week intervention phase to include, specific to assigned condition, medication, PN, DE, assessments, and medical management. The screening phase will differ in the length of time needed to complete eligibility assessments, random assignment, and to complete medication induction in the VI and PNV conditions. Induction will be scheduled to occur within 4 weeks of discharge. Screening assessments will include the collection of laboratory samples and medical assessments to ensure participant safety. Confirmation of opioid-free status (UDS and naloxone challenge) before medication induction will take approximately two hours. Assessment visits at 1, 3, 6, 7, and 12-months will take about 30-60 minutes depending on the scheduled assessments. Medical management visits will last from 20–60 minutes and will include collection of UDS and other short measures of status and well-being. PN sessions are expected to take about 60 minutes. DE sessions will take about 20 minutes.

5.3 Study Population

Participants will be 150 individuals meeting DSM-5 criteria for opioid use disorders who are 18 years and older, have been detoxified from opioids in the Bernalillo County Metropolitan Detention Center and meet eligibility criteria.

5.3.1 Inclusion Criteria

Study participants *must*:

- 1. Be at least 18 years of age or older,
- 2. Meet criteria for DSM-5 opioid use disorders,
- 3. Be detained for at least 48 hours,
- 4. Have an expected release date within one year,
- 5. Plan to reside in area after release,
- 6. Have at least one instance of relapse to opioid use after a period of abstinence.

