2.2 Study Design

This four-year randomized, open-label trial will examine the feasibility, efficacy, and net economic benefits of VI for opioid addiction delivered with and without a platform of PN provided for six months compared against a DE condition. Before release from jail, participants in the VI and PNV conditions will receive their first Vivitrol injection (and those in the PNV condition will meet with a Patient Navigator) and will then be scheduled for medication management sessions twice monthly for months 1-3, with monthly injections in months 4-6. Participants in the PNV condition will meet with a PN who will provide behavioral assistance to overcome possible barriers to community outpatient treatment and will be provided with a schedule of possible community treatment programs. Participants in the DE condition will receive education designed to reduce the likelihood of overdose on the same schedule as the VI and PNV groups. All participants will receive weekly study phone calls to assess well being and possible adverse events.

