5.4 Participant Recruitment

Recruitment through a close collaboration with the Bernalillo County Metropolitan Detention Center (BCMDC) staff, combined with IRB-approved presentations and posted announcements in the jail facilities will proceed until 150 participants are recruited, consented, and randomized. Given the potential recruitment pool of more than 80 individuals per month, it is expected that an average of 6-8 individuals will be randomized per month across the 20-month enrollment period. Based on prior evidence in similar trials, refusals and early (pre-randomization) dropouts will account for approximately 20% of individuals presenting for screening.

Recruitment plans include hypervigilence to the issue of voluntariness. All BCMDC and study staff will be extensively trained on this issue to ensure that their actions and words do not convey any level of coercion. Training will include a discussion of the fact that treatment and study compliance are optimized when participants have the opportunity to consider the study, ask questions, and provide voluntary consent to participate. Furthermore, all recruitment documents and the ICF will emphasize that decisions whether or not to participate are solely up to the individuals, that the decision will not affect the treatment or possible treatment to which the individual is eligible, that participation/non-participation will not affect the sentence, release, probation, or any other aspect of the individual's incarceration.

The main method of recruitment will be announcements of the study made to inmates in the Bernalillo County Metropolitan Detention Center (BCMDC). An informational flyer will be provided to arrestees who are within 4 weeks of release and have been detoxified from opioid use. Individuals who convey interest in this study to jail staff will be referred to study staff. If still interested after receiving a description of this study, study candidates will complete a consent process that includes an detailed explanation of the study, risks and benefits, and that study

participation is voluntary and will have no effect on a participant's sentence, jail term, probation, parole, or release.

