6.1 Primary Outcome Measure

The primary outcomes will be opioid use and a DSM-5 diagnosis of opioid use disorder 6 months after randomization.

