7.2 Screening

The study team will provide a basic description of the study to interested individuals who respond to IRB-approved flyers and announcements at BCMDC. Study staff will verify pre-eligibility status of each study candidate with jail staff (e.g., has completed opioid detoxification, jail term and expected release date). Individuals determined as pre-eligible will be scheduled for a consent/screening appointment. Screening will begin with the informed consent process. A complete medical history and physical exam will occur after consent. Participants will be randomized to study condition when results of all assessments, including blood chemistries and ECG, are obtained and eligibility is confirmed. Screening will take ~4 hours, excluding review of lab results. This process may occur over multiple days.

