10.1 Primary Outcome

The primary outcomes of opioid use and a DSM-5 diagnosis of opiate use disorder 6 months after randomization.

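### The one-year release criterion conflicts with the four-week timing used elsewhere, so a participant could be randomised, and even read for the primary outcome, well before release or the first injection

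*Combined protocol and SAP*

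**What the plan says.** The relevant rules are in separate sections of the combined protocol and SAP.

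- **Eligibility (5.3.1, criterion 4):** participants must "Have an expected release date within one year".
- **Recruitment (5.4):** "An informational flyer will be provided to arrestees who are within 4 weeks of release and have been detoxified from opioid use".
- **Randomisation (7.2):** "Participants will be randomized to study condition when results of all assessments, including blood chemistries and ECG, are obtained and eligibility is confirmed". Nothing in 7.2 or 7.3 ties this to the release date.
- **First injection (2.2 and 5.2):** it is given in custody ("Before release from jail, participants in the VI and PNV conditions will receive their first Vivitrol injection") and timed by release ("Induction will be scheduled to occur within 4 weeks of discharge"). Section 5.2 also gives "a projected 2-4 weeks for screening/baseline assessments and medication induction".
- **Primary outcome (6.1):** "The primary outcomes will be opioid use and a DSM-5 diagnosis of opioid use disorder 6 months after randomization". Section 10.1 repeats the anchor: "DSM-5 diagnosis of opiate use disorder 6 months after randomization".
- **Other anchors for the 6-month point:** after the intervention (2.4 Analyses, 4.3.1); post treatment (10.4.2); post-release, at the end of the intervention phase (4.3.2, 6.2 and 10.2, for the secondary drug-use measures). Table 1 in section 8.0 lists the month 1, 3, 6, 7 and 12 assessments under its post-release heading.
- **Losses before treatment:** 7.3 replaces people who leave before induction or the comparable behavioural time point. Section 10.0 analyses only those with at least one dose (VI, PNV) or one education session (DE).

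**The concern.** The trial asks whether treatment started in jail prevents relapse after release (4.3, Aim 2). For the primary read to answer that, the participant must have been released and have had the chance to start the assigned condition. Criterion 4 guarantees neither, because eligibility and randomisation are not tied to release while induction is.

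Two things are at stake. First, under the randomisation anchor, a read in index custody says nothing about relapse in the community. Second, under any anchor, a long wait between randomisation and first treatment gives time for people to drop out. Those people are replaced and not analysed, so the compared groups are no longer simply those randomised. The loss may also differ by arm. Only the medication arms must pass a naloxone challenge first (7.4.1), and the 4-week rule covers induction only: patient navigation and drug education need only begin before discharge (5.1).

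**Working it through.** The plan states no figure on this point, so there is nothing to reproduce. The check is timeline arithmetic.

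**Inputs.** Randomisation is week 0 and release is week R. Criterion 4 allows R up to about 52; eligibility is confirmed at randomisation (7.2), so the year is counted from there. The primary read is A = 6 months = (365.25/12 × 6)/7 = 26.1 weeks (6.1, 10.1). The induction window opens 4 weeks before release (5.2), at week max(0, R − 4). The opioid-use outcome looks back 30 days = 30/7 = 4.3 weeks (2.4 Analyses). Actual release is taken to equal expected release.

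**Thresholds under the randomisation anchor.**

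- In index custody at the read if R > A, that is R > 26.1 weeks.
- Read before the induction window opens if R − 4 > A, that is R > 30.1 weeks.
- Part of the 30-day look-back in custody if R > A − 4.3, that is R > 21.8 weeks.

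| Release (week R) | Induction window opens (week) | Weeks in community before read (26.1 − R) | State at the read |
|---|---|---|---|
| 4 | 0 | 22.1 | released |
| 8 | 4 | 18.1 | released |
| 28 | 24 | −1.9 | in custody, induction possible |
| 36 | 32 | −9.9 | in custody, induction window not open |
| 52 | 48 | −25.9 | in custody, induction window not open |

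**Under a release anchor.** The visit follows release by definition, so no read falls in index custody for any R. The wait from randomisation to the opening of the induction window is still R − 4, up to 52 − 4 = 48 weeks.

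**If randomisation occurs only when release is expected within 4 weeks.** The read falls at least 26.1 − 4 = 22.1 weeks after release even under the randomisation anchor, and no one is uninjected merely because of timing.

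**The case against.** The strongest reply is that the projected schedule already prevents this. The 2-4 weeks in section 5.2 cover screening and induction, and that section counts random assignment within the screening phase. Adding the 4-week induction limit puts randomisation at most about 4 + 4 = 8 weeks before release, leaving about 26.1 − 8 = 18.1 weeks in the community before the read. Flyers go to people within 4 weeks of release, staff check the expected release date before the consent visit (7.2), and post-release assessments are held at university clinics (5.5).

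This stands as a description of intent: if that schedule is followed, no one is read in index custody. It does not stand as a safeguard. The 2-4 weeks are a projection. The 4-week limit applies to the flyer, while announcements, presentations and posted notices carry none. Section 7.2 gives no release cut-off, so the only one on record is criterion 4. Exclusion 6 concerns pending legal action during the 24-week intervention, not a longer current term.

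The post-release anchors also count. Adopting one would remove the in-custody read, though not the wait before induction.

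A reader might go further in two ways that the documents do not support.

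- **That a large share will be affected.** If release were uniform over one year (52.2 weeks), (52.2 − 26.1)/52.2 = 50% would be in custody at the read and (52.2 − 30.1)/52.2 = 42% would not have reached the induction window. The documents give no such distribution, and they point to short stays: 4.1.1 describes jail stays of a few days to several months, and 5.2 and 5.4 assume imminent release.
- **That untreated participants must pull the arms together.** Section 10.0 excludes medication-arm participants who never receive a dose. It sets no date for that dose, so someone injected after an early read could still enter the set. The direction of any bias is therefore not settled.

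**Conclusion.** The concern holds as an unreconciled contradiction that leaves a gap in the rules. It is not a prediction that participants will be read in custody. Taken literally, criterion 4 with sections 7.2, 6.1 and 10.1 permits a primary read in index custody (release after about 26 weeks) or before the induction window opens (after about 30 weeks), and no eligibility or randomisation rule blocks it. Under a post-release anchor the in-custody read disappears. What remains is a wait of up to about 48 weeks before induction opens, with losses replaced and excluded from analysis.

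The share affected cannot be estimated from the documents. It is 0% if all recruits are within 4 weeks of release, and otherwise depends on how far sites use the one-year allowance. The week thresholds assume release on the expected date. The point should be fixed because the correction is cheap and protects the randomised comparison; nothing shows that the design fails in practice.

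**What to change.** Reconcile sections 5.3.1, 5.2 and 5.4 so that they state one release window. The one-year limit may stay for pre-screening. Amend 7.2 so that randomisation waits until expected release falls within the induction window the protocol already uses, and re-confirm eligibility at that point. Then use one anchor for the 6-month primary outcome in 2.4 (Analyses), 4.3.1, 6.1, 10.1 and 10.4.2, and align the secondary measures in 4.3.2, 6.2 and 10.2 with it.

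The cost is a short amendment, with two drawbacks. People with distant release dates wait to be randomised. A tight window also leaves less slack: screening and induction are projected at 2-4 weeks, so someone released unexpectedly early may miss in-jail induction and be replaced under 7.3. Starting screening earlier and delaying only randomisation eases this. Section 5.4 gives a pool of more than 80 people per month against 6-8 randomised, which suggests that the tighter rule is feasible, although how that pool was defined is not stated.

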5.3.2 Exclusion Criteria

Study participants *must not*:

- 1. Have a medical (e.g., liver failure, congestive heart failure) or psychiatric condition (e.g., suicidal ideation, psychosis) that would make participation unsafe in the judgment of the medical staff or the PI,
- 2. Have current or chronic pain or have plans to undergo pain treatment/therapy,
- 3. Have known sensitivity to naltrexone or naloxone,
- 4. Have participated in an investigational drug study within the past 30 days prior to screening,
- 5. Be a nursing or pregnant female, or not agree to use a medically acceptable form of birth control such as oral contraceptives, barrier (diaphragm or condom), levonorgestrel implant, intra-uterine progesterone contraceptives system, medroxyprogesterone acetate contraceptive injection, or complete abstinence. Females who become pregnant during the course of the study will be withdrawn from the study and, if requested, will be provided with referrals for drug treatment and/or medical care,
- 6. Have any pending legal action that could prohibit continued participation for the 24-week intervention period of the study, such as legal proceedings that could possibly result in incarceration,
- 7. Have a current pattern of alcohol, benzodiazepine, or other depressant or sedative hypnotic use, as determined by the study physician which would preclude safe participation in the study.

5.4 Participant Recruitment

Recruitment through a close collaboration with the Bernalillo County Metropolitan Detention Center (BCMDC) staff, combined with IRB-approved presentations and posted announcements in the jail facilities will proceed until 150 participants are recruited, consented, and randomized. Given the potential recruitment pool of more than 80 individuals per month, it is expected that an average of 6-8 individuals will be randomized per month across the 20-month enrollment period. Based on prior evidence in similar trials, refusals and early (pre-randomization) dropouts will account for approximately 20% of individuals presenting for screening.

Recruitment plans include hypervigilence to the issue of voluntariness. All BCMDC and study staff will be extensively trained on this issue to ensure that their actions and words do not convey any level of coercion. Training will include a discussion of the fact that treatment and study compliance are optimized when participants have the opportunity to consider the study, ask questions, and provide voluntary consent to participate. Furthermore, all recruitment documents and the ICF will emphasize that decisions whether or not to participate are solely up to the individuals, that the decision will not affect the treatment or possible treatment to which the individual is eligible, that participation/non-participation will not affect the sentence, release, probation, or any other aspect of the individual's incarceration.

The main method of recruitment will be announcements of the study made to inmates in the Bernalillo County Metropolitan Detention Center (BCMDC). An informational flyer will be provided to arrestees who are within 4 weeks of release and have been detoxified from opioid use. Individuals who convey interest in this study to jail staff will be referred to study staff. If still interested after receiving a description of this study, study candidates will complete a consent process that includes an detailed explanation of the study, risks and benefits, and that study

participation is voluntary and will have no effect on a participant's sentence, jail term, probation, parole, or release.

Treatment procedures for jail inmates: Offenders are detoxified (if necessary) under physician supervision within the jail setting. After this, they are moved to the general inmate population but have follow-up visits with the jail physicians. While in custody, they may opt to pursue participation in available onsite treatment programs.

Prior to release, a case worker from Inmate Services meets with the inmate and may make a referral to a community-based program, which can be either drug-free residential or outpatient, depending on inmates' needs and preferences. Show-up rates in the community tend to be quite low, but transportation directly from the jail to treatment programs has resulted in improved admission rates.

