5.5 Study Sites

UCLA Integrated Substance Abuse Program (ISAP). The leadership, data management, and analysis portions of the proposed project will occur at UCLA ISAP in Los Angeles.

[name], will be the physician PI for this study. He has extensive experience in both the use of Vivitrol and behavioral treatments. He will be involved in supervision of the medical aspects of this study, randomization, and will meet regularly with other study personnel. He has conducted over a dozen clinical trials using MAT and will be responsible for medical team training. More recently, he has conducted research using Vivitrol and has been instrumental in the training of other ISAP medical personnel on the Vivitrol injection.

For this project, the primary sites for recruitment, data collection, and treatment services are the Bernalillo County Metropolitan Detention Center and the University of New Mexico, Department of Psychiatry.

Bernalillo County Metropolitan Detention Center (BCMDC). Recruitment and induction will occur at the jail sites in the BCMDC System. The jail facility houses sentenced and unsentenced inmates. The types of inmates housed here are general population, violent/assaultive offenders, psychiatric, and inmates needing medical services. This facility is staffed with Sheriff Service Technicians, intake and release specialists, medical service staff contracted by the County Behavioral Health Department, and clerical support staff. Bernalillo County opened the MDC facility in 2003. Currently, the MDC averages about 40,000 bookings per year, with an average daily population of 2,636. Males account for 87% of the inmate population. With regard to race/ethnicity, 54% are Hispanic, 23% White-Non-Hispanic, 12% American Indian, 9% African-American, 0.4% Asian, and 1.7% are categorized as "Other." Currently the MDC detoxifies an average of 758 individuals monthly—412 from alcohol and 346 from opiates.

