7.3 Random Assignment

Eligible participants will be randomly assigned to study condition (VI, PNV, DE) in a 1:1:1 strategy using an urn randomization procedure (Stout et al., 1994) to provide multivariate balance across two characteristics correlated with outcomes in addiction treatment trials: type of opioid (heroin or prescription drug) and gender.

Individuals who terminate participation before induction onto the assigned medication (or similar time-point for behavioral assignments) will be replaced. Those terminating after VI induction or provision of the first DE session will not be replaced and will be counted as "treatment failures" (in an intent-to-treat scenario).

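### The recruitment window and the in-jail induction time are not reconciled, and with no minimum time to release at randomisation, loss before first treatment can be larger in VI and PNV and go unseen

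*Combined protocol and SAP*

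**What the plan says.** **Approach.** Section 5.4: "An informational flyer will be provided to arrestees who are within 4 weeks of release and have been detoxified from opioid use". The same section says "The main method of recruitment will be announcements of the study made to inmates", and no time limit is attached to that route. Inclusion criterion 4 (Section 5.3.1) reads "Have an expected release date within one year". That is a maximum; no criterion sets a minimum.

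**Duration and place.** Section 5.2 gives a "projected 2-4 weeks for screening/baseline assessments and medication induction" and schedules induction within 4 weeks of discharge. Section 5.1: "Before discharge from jail, participants randomized to one of two medication conditions (VI, PNV) receive Vivitrol". Section 5.5: "Recruitment and induction will occur at the jail sites in the BCMDC System".

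**Order of steps.** Under Section 7.2, staff check the expected release date with the jail before the consent visit, and randomisation follows once all screening results are in and eligibility is confirmed. VI and PNV participants then have a naloxone challenge and one day of oral naltrexone before the injection (Sections 2.4 Interventions and 7.4.1). DE participants also start before discharge (5.1), with a session of about 20 minutes (5.2).

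**Handling of early loss.** Section 7.3: "Individuals who terminate participation before induction onto the assigned medication (or similar time-point for behavioral assignments) will be replaced". Those who leave after the injection, or after the first DE session, are not replaced and count as failures. Section 10.0 limits the intent-to-treat set to randomised participants with at least one dose or one DE session.

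**The concern.** Two things are wrong. First, the time figures do not fit together. A person reached by flyer has between 0 and 4 weeks of custody left, the process is projected at 2 to 4 weeks, and for VI and PNV it has to end in the jail. A person with little time left can be screened, found eligible and randomised, because nothing turns the verified release date into a condition for randomisation.

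Second, the path from randomisation to first treatment is longer in VI and PNV than in DE. A participant released during that interval, and so not inducted in the jail, falls under the replacement rule and outside the analysis set. Suppose two participants are both released two days after assignment. The DE participant who has already had a session stays in the analysis and, if then lost, counts as a failure. The VI participant still waiting for the injection is replaced and not counted. The compared groups could then differ in remaining custody and in whatever goes with it. Replacement restores the group sizes, so the difference would not show in the final counts.

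**Working it through.** **The plan's own figure.** 150 participants over 20 months is 150/20 = 7.5 a month, inside the stated 6-8 (Section 5.4). No rate of release before first treatment is given anywhere, so what follows are scenarios.

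**Notation.** R = days of custody left when approached; S = days from approach to injection; g = days from randomisation to injection; b = days from randomisation to first DE session. A candidate is randomised if R ≥ S − g. A VI/PNV participant is lost if S − g ≤ R < S; a DE participant is lost if S − g ≤ R < S − g + b.

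**Inputs from the documents.** R up to 28 days for the flyer route (5.4); S of 14-28 days (5.2); g of at least about one day (7.4.1).

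**Assumptions.** Uniform distributions; R and S independent; g = 2 days; b = 1 day; release date not used as a filter.

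**Scenario A: R uniform 0-28, S uniform 14-28 (mean 21).**
- P(randomised) = (28 − 21 + g)/28 = (7 + 2)/28 = 32.1%. The other 67.9% are released before allocation, equally in all arms.
- Loss after randomisation, VI/PNV: g/(7 + g) = 2/9 = 22.2%.
- Loss after randomisation, DE: b/(7 + g) = 1/9 = 11.1%.

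**Scenario B: R uniform 0-28, S = 14.**
- VI/PNV: g/(14 + g) = 2/16 = 12.5%. DE: b/(14 + g) = 1/16 = 6.3%.

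**Scenario C: R uniform 14-28, S = 14.**
- Everyone has R ≥ S, so the loss is 0% in every arm.

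| Scenario | Released before S, all candidates | Lost after randomisation, VI/PNV | Lost after randomisation, DE |
|---|---|---|---|
| A | 1 − 7/28 = 75% | 22.2% | 11.1% |
| B | 14/28 = 50% | 12.5% | 6.3% |
| C | 0% | 0% | 0% |

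**Sensitivity to the gap.** In A with g = 3, the losses are 3/10 = 30% and 1/10 = 10%. If the DE session is held on the day of assignment (b = 0), DE loss is 0% in every scenario. The documents do not say when the session is held.

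**Effect on numbers.** At 22.2% loss, 50/(1 − 0.222) ≈ 64 people must be randomised for every 50 injected. Supply would still suffice: 80 candidates a month × 0.8 (the stated 20% loss before randomisation) × 0.25 (scenario A) = 16 a month, against 7.5 needed.

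**The case against.** The strongest reply has four parts.

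- **The flyer is one channel.** Announcements are the main route and have no 4-week limit, and criterion 4 admits people up to a year from release. This stands. A reader might infer that candidates are approached only in the last 4 weeks; the documents do not say so.
- **Most release in these scenarios comes before allocation.** This also stands. Release during screening cannot unbalance the arms, so the 50% and 75% in the second column of the table are no measure of arm-specific loss. DE must also begin before discharge, and its losses before the first session are replaced too. The tempting reading that the loss falls on VI and PNV alone is therefore not supported; the supportable statement is that it can be larger there.
- **The 2-4 weeks is a projection.** Screening takes about 4 hours of contact (7.2) and confirming opioid-free status about 2 hours (5.2), so 14 days is not a hard floor. This stands too, and it is a reason to let the site set the number of days.
- **Staff already verify the release date.** True, and in practice they may not bring forward someone about to leave. But Section 7.2 gives no threshold, and the jail holds unsentenced inmates (5.5), whose dates may shift.

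The reply leaves the post-randomisation gap, the replacement rule and the restricted analysis set untouched.

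**Conclusion.** The point holds in a limited form. Sections 5.1, 5.2, 5.3.1, 5.4 and 5.5 must be reconciled on when people are approached and how much custody must remain. Followed as written, the plan can randomise people with too little time left to be inducted, and Sections 7.3 and 10.0 would then remove them from the comparison, possibly at different rates by arm.

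The size is unknown. It runs from 0% in all arms (14-28 days left, 14 needed) to about 22% in VI/PNV against 11% in DE (0-28 days left, 14-28 needed, gaps of 2 days and 1 day), and is greater if the medication gap is longer. These figures rest on uniform, independent times and on the release date not being used as a filter. The documents support neither a statement that many will be released first nor a threat to enrolment. The risk is selection bias, and its net effect on the six-month outcomes cannot be derived from the documents.

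**What to change.** 1. Add one condition for randomisation, identical in all three arms: the expected release date verified with jail staff must leave at least the number of days the site needs to complete pre-induction. The site sets and records that number.
2. State in Section 5.4 that consent and screening may begin earlier than 4 weeks before expected release, as criterion 4 already permits, and align Sections 5.2 and 5.3.1 with it.
3. State how a participant released before first treatment is handled, and keep all randomised participants in the primary analysis. Section 10.0 already treats dropouts as retaining the diagnosis at six months, so the rule for that outcome exists. The dosed-or-session set can remain as a supporting analysis.
4. Report, by arm, the number lost between randomisation and first treatment, with reasons and the days from assignment to release.

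The induction procedure and its timing relative to discharge stay as they are.

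**Cost.** Wording in Sections 5.2, 5.3.1, 5.4, 7.2, 7.3 and 10.0, and one extra row in the participant flow table. Some very short-stay inmates will not be randomised. Unexpected releases will still occur, which is why items 3 and 4 are needed alongside item 1. Keeping untreated participants in the primary analysis may dilute the estimated effect of the injection.
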